6.1.7.1 Management of Tumor Lysis Syndrome (TLS)

There is a potential risk for TLS in subjects with AML, especially in those with elevated leukocyte count, circulating blasts, elevated pretreatment LDH levels, renal dysfunction, and dehydration. In addition, on-target effect of venetoclax could lead to rapid cell death and pose a risk of TLS. To mitigate the risk for TLS all subjects enrolled in the study will need TLS prophylaxis and monitoring. Prophylactic reductions of potassium, inorganic phosphorus or uric acid above normal range are recommended prior to beginning study treatment and continue based on the ongoing risk of TLS. For subjects at higher risk for TLS (i.e., circulating blasts, high burden of leukemia involvement in bone marrow, elevated pretreatment LDH levels, or renal dysfunction), additional mitigation measures including more intensive laboratory monitoring and interventions should be implemented. Lower starting dose of venetoclax/placebo may be considered (i.e., 50 mg).

Below are the minimum requirements for TLS prophylaxis and management for all subjects enrolled into the study. All other prophylaxis and monitoring procedures for TLS will be implemented as per regional guidelines/institutional standards:

- All subjects will be hospitalized on or before Day 1 of Cycle 1 prior to administration of the initial dose of study treatment and remain in the hospital for at least for 24 hours after reaching the final dose of venetoclax.
- All subjects must receive uric acid reducing agent, adequate oral and intravenous hydration as tolerated while monitoring the fluid status of the subject prior to and during the ramp up of venetoclax/placebo. The uric acid reducing agent, type of fluids and the rate of infusion will be determined by the investigator based on regional standards or institutional guidelines.

- TLS chemistry tests to be drawn (calcium, inorganic phosphorus, potassium, uric acid, and creatinine) on the first day of venetoclax/placebo dosing and each day of a new dose at 0 (within 4 hours prior to dosing) and 6 – 8 hours post dose.
- Additional laboratory assessments may be performed, per investigator discretion, post-dose during ramp up and up to 48 hours after reaching final dose if clinically indicated.
- Abnormal chemistry tests during ramp up should be corrected promptly.

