6.0 Analysis Conventions

General Considerations

Unless otherwise noted, for all statistical analyses, statistical significance will be determined by a two-sided P value ≤ 0.05 . The date of randomization is defined as the date that the IVRS/IWRS issues a randomization number.

Definition of Study Drug

Unless otherwise specified, the study drug in this document refers to venetoclax/placebo and LDAC. The first dose date of study drug is defined as the date the 1st dose of venetoclax/placebo or LDAC, whichever occurs first, is administered. The last dose date of study drug is defined as the date the last dose of venetoclax/placebo or LDAC, whichever occurs later, is administered.

Definition of Baseline

All baseline summary statistics and analyses will be based on characteristics prior to the initiation of any component of study drug (or randomization for non-treated subjects). Unless otherwise stated, baseline for a given variable will be defined as the last value for that variable obtained prior to the first dose of any component of study drug or randomization for non-treated subjects.

Definition of Final Observation

The final observation in [Table 2](#) and [Table 3](#) is defined as the last non-missing observation collected after the first dose of study drug to the last dose of study drug + 30 days.

Definition of Data Cutoff Date

The data cutoff date for interim analysis (IA) will be the projected date of the 100th death occurred in the full analysis set. The data cutoff date for final analysis (FA) will be the projected date of the 133th death occurred in the full analysis set.

The same data cutoff date will be implemented for both efficacy and safety analyses.

Stratification Factor for Efficacy Analyses

AML status (secondary, de novo) and age ($18 < 75, \geq 75$) will be used in all stratified analyses of the efficacy endpoints. The stratification factor value under which the subject is randomized by the IVRS/IWRS will be used in the efficacy analyses.

Definition of Cycle Rx Days in Each Cycle

Cycle Rx Days for each cycle are calculated for each time point relative to first dose of study drug in each cycle. The day of the first dose of study drug in each cycle is defined as Cycle Rx Day 1, while the day prior to the first dose of study drug is defined as Cycle Rx Day -1 (there is no Cycle Rx Day 0).

Definition of Analysis Windows

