All time points and corresponding time windows are defined for each cycle are based on Cycle Rx Day 1 of each cycle.

For visit-wise clinical laboratory analyses, vital signs analyses, and quality of life analyses, the time windows specified in [Table 2](#) and [Table 3](#) describe how efficacy and safety data are assigned to protocol specified visits respectively. Analysis time windows are constructed using the following algorithm:

- Determine the nominal Cycle Rx day for each scheduled visit.
- Determine the window around a specific nominal Cycle Rx day as in [Table 2](#) and [Table 3](#).
- If more than one assessment are included in a time window of the assessment, the one closest to the nominal day should be used. If there are two observations with equal distance to the nominal day, the later one will be used in analyses. If multiple values are collected on the same day, the arithmetic average will be calculated and used as the value of that day for the mean change analyses.

- For analysis of tumor lysis syndrome (TLS) laboratory variables meeting the Howard criteria where multiple values were collected over the course of a day (within 4 hours prior to dosing and 6 – 8 hours post dose), all values will be used and no averages will be taken.
- For analysis of liver enzyme laboratory variables meeting criteria for potential drug-induced liver injury, all values will be used and no averages will be taken.
- For laboratory shift tables, the Common Terminology Criteria (CTC) grade will be assigned based on all observed laboratory values and no averages will be taken. If multiple grades are collected on the same day, the worst grade will be used as the value of that day for the shift table analyses.

Table 2. Time Windows for Analysis of Hematology, Chemistry, and Vital Signs Parameters

Scheduled Visit	Nominal Cycle Rx Day	Time Window (Cycle Rx Day Range)
Baseline	≤ 1	See the baseline definition (Section 6.0)
Cycle 1 Day 2	2	[2]
Cycle 1 Day 3	3	[3]
Cycle 1 Day 4	4	[4]
Cycle 1 Day 5	5	[5]
Cycle 1 Day 8	8	[6, 11]
Cycle 1 Day 15	15	[12, 18]
Cycle 1 Day 21	21	[19, 25]
Cycle 2 Day 1	1	[-3, 10]
Every Cycle from Cycle 3 Day 1	1	[-10, 10]
Final Observation	NA	The last non-missing observation collected after the first dose of study drug to the last dose of study drug + 30 days

Note: Hematology and chemistry samples will be collected at visits specified in the protocol. Vital signs will be measured at visits specified in the protocol.

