11.3.2 Analyses of Shift from Baseline in Clinical Laboratory Data

For shifts relative to National Cancer Institute Common Toxicity Criteria for Adverse Events (NCI CTCAE version 4.03), baseline and post-baseline laboratory observations will be categorized as grade 0, grade 1, grade 2, grade 3, or grade 4 according to NCI CTCAE grade version 4.03.

The baseline and final grades will be defined respectively as the grade of the last measurement collected on or prior to the first dose of study drug (or randomization for non-treated subjects), and as the last post-baseline measurement collected no more than 30 days after the last dose of study drug.

The maximum NCI toxicity grade value is the value with highest NCI toxicity grade collected after the first dose of study drug and within 30 days following the last dose of

study drug. In cases where multiple values are collected on the same day, the maximum grade value will be selected as the value for that day.

For each variable, shift tables will be generated that cross tabulate the number of subjects with baseline values of grade 0, grade 1, grade 2, grade 3, or grade 4 versus maximum post-baseline/final observations of grade 0, grade 1, grade 2, grade 3, or grade 4. All treated subjects will be included in the cross tabulation regardless whether baseline or post-baseline measurements are collected.

The separate laboratory shifts tables, based on the two criteria below will be generated for each laboratory tests related to CTCAE:

1. Shifts from Grade 0 (Normal) at baseline to grade 1 - 4 Post-baseline (maximum) and worsening from an abnormal baseline value of at least one grade up post-baseline (maximum)
2. Shifts from Grade 0 - 2 at baseline to grade 3 or 4 Post-baseline (maximum) and from grade 3 at baseline value to Grade 4 post-baseline (maximum).

Detailed listings of data for subjects experiencing NCI CTCAE grade 3 to 4 blood chemistry and hematology values will be provided. All measurements collected, regardless of the number of days after the last dose of study drug will be included in these listings.

Number and percentage of subjects with liver Enzyme value meeting the criteria for potential drug-induced liver injury ($ALT > 3 \times ULN$ or $AST > 3 \times ULN$ and $TBILI > 2 \times ULN$ within 72 hours of each other) will be presented.

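### SAP 11.3.2 takes the shift-table baseline on or before the first dose, against the protocol and SAP 6.0; read by date, this lets the 6–8 hour post-dose Day 1 chemistry serve as baseline

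*SAP*

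**What the plan says.** **The shift-table rule.** SAP 11.3.2 defines the baseline grade as "the grade of the last measurement collected on or prior to the first dose of study drug (or randomization for non-treated subjects". The post-baseline maximum in the same section is the highest grade after the first dose and up to 30 days after the last.

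**The general rule.** SAP 6.0 defines baseline, unless otherwise stated, as "the last value for that variable obtained prior to the first dose of any component of study drug or randomization for non-treated subjects". SAP 11.3, the parent section, says that laboratory baseline is the one defined in Section 6.0. Protocol 8.1.7.5, describing the same baseline grades for the same shifts, also requires a measurement before the first dose. Protocol 5.1.3 places the baseline laboratory draw on Cycle 1 Day 1 before treatment.

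**Several values on one day.** SAP 6.0 says of the shift tables: "If multiple grades are collected on the same day, the worst grade will be used as the value of that day". It does not exempt the baseline day. SAP 11.3.2 has a similar sentence, "the maximum grade value will be selected as the value for that day", but in its paragraph on the post-baseline maximum.

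**What is drawn on Day 1.** Protocol 6.1.7.1 sets as a minimum for all subjects: "TLS chemistry tests to be drawn (calcium, inorganic phosphorus, potassium, uric acid, and creatinine) on the first day of venetoclax/placebo dosing". There are two draws, one in the 4 hours before the dose and one 6–8 hours after it, repeated whenever the dose is raised. Protocol 5.5.1 and 5.5.4 put venetoclax or placebo before LDAC, so the later draw falls after the first dose of any study drug.

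**The concern.** Baseline in a shift table should be untouched by treatment. SAP 11.3.2 departs from the other definitions by one word, and on the first dosing day that word decides on which side of the shift a required post-dose sample falls. Section 6.0 gives way where a different baseline is stated, and 11.3.2 states one, so a programmer could reasonably follow 11.3.2.

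If the 6–8 hour sample becomes baseline, a grade change between the two Day 1 draws is absorbed into the starting value. That is the period the tumor lysis monitoring is meant to watch. The shift tables give by-arm counts of grade change in each single analyte, and those counts could understate early worsening.

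**Working it through.** The plan states no figure to reproduce. The check is a comparison of definitions, then an enumeration of the rule.

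**1. The definitions side by side**

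| Place | Baseline relative to first dose |
|---|---|
| Protocol 8.1.7.5 (shift grades) | before |
| SAP 6.0 (general) | before |
| SAP 11.3 (laboratory) | as in SAP 6.0 |
| SAP 11.3.2 (shift grades) | on or before |

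**2. What *on* can mean.** By clock time, a sample taken 6–8 hours after the dose is after it. It belongs to the post-baseline maximum, and there is no problem. By date, it is collected on the day of the first dose and qualifies as baseline. Three features make the date reading plausible. SAP 6.0 defines the first dose by its date. SAP Tables 4 and 5 use the same wording with the data cutoff date. SAP Table 2 gives baseline a nominal day of 1 or less and opens its first post-baseline window on Day 2, although that baseline row refers back to Section 6.0. The shift-table text has no collection-time rule.

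**3. How the post-dose sample is selected under the date reading.** There are two routes. It is the last measurement of the qualifying day, which is enough without any same-day rule. Or, if the same-day rule of SAP 6.0 is carried to the baseline day, it is selected whenever it is the worse of the two.

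**4. Example (assumed grades).** Pre-dose grade 0, 6–8 hour grade 3, later maximum grade 2.
- Pre-dose baseline: 0 to 3. This counts under criterion 1 of SAP 11.3.2 (at least one grade worse) and criterion 2 (0–2 to 3–4, or 3 to 4).
- Date reading: baseline 3, maximum at most 3. It counts under neither.

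**5. Enumeration.** Let *p* be the pre-dose Day 1 grade, *q* the post-dose Day 1 grade and *r* the later maximum, each 0 to 4, giving 5 × 5 × 5 = 125 combinations.

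*Pre-dose baseline* (*p* against max(*q*, *r*)):
- Criterion 1: the sum over *p* of 25 − (*p* + 1)² is 24 + 21 + 16 + 9 + 0 = 70.
- Criterion 2: 3 × (25 − 9) + (25 − 16) = 48 + 9 = 57.

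*Date reading with worst of day* (baseline max(*p*, *q*)):
- Criterion 1 needs *r* above both: 0 + 1 + 4 + 9 + 16 = 30 remain, so 70 − 30 = 40 are lost.
- Criterion 2: 9 × 2 + 7 × 1 = 25 remain, so 57 − 25 = 32 are lost.
- None is gained. The result is the same whether or not *q* also counts in the post-baseline maximum.

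*Date reading with last value only* (baseline *q*):
- Criterion 1: *r* > *q* in 10 of 25 pairs, times 5 values of *p*, gives 50. The 30 combinations above are among them, so again 40 are lost, but 50 − 30 = 20 are gained.
- Criterion 2: (3 × 2 + 1) × 5 = 35. The 25 above are among them, so 32 are lost and 35 − 25 = 10 are gained.
- The gains arise where the post-dose grade is better than the pre-dose grade.

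These are unweighted combinations of grades, not probabilities. They show how the rule behaves, and the documents give no grade frequencies from which to estimate an effect in the trial.

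**The case against.** The best defence is that 11.3.2 refers to the first dose, not to its date, although SAP 6.0 has a separate term for that date. A sample drawn hours after a dose is neither on nor before it. The next paragraph of 11.3.2 assigns values after the first dose to the post-baseline maximum, so the date reading puts one sample on both sides of the shift. The parent section points to the strict definition, and the protocol is strict throughout. This stands as an argument that clock time may be intended. It does not remove the conflict, because by clock time *on* adds almost nothing, and the SAP does not say which reading applies.

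A reader might infer that the Day 1 baseline simply is the worse of the two draws. The documents do not say so. Section 11.3.2 speaks of the last measurement, and only the general sentence in SAP 6.0 could bring in the worst grade.

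A reader might also infer that treatment-caused lysis would be hidden. That goes too far. The laboratory TLS count in 11.3.2 starts after the first dose, uses every value under SAP 6.0 and does not use this baseline. The grade 3–4 listings include all measurements. SAP Table 9 summarizes TLS adverse events, and SAP 11.1 treats events starting on the first-dose date as treatment-emergent. These outputs compensate only in part. The TLS count needs two abnormalities within 24 hours and omits creatinine. The listings leave out grade 1–2 worsening and are not counts of shifts. Under protocol 6.1.1.1 a laboratory change is an adverse event only under stated conditions.

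**Conclusion.** The point holds as a conflict between definitions with a possible effect on the shift tables. SAP 11.3.2 contradicts protocol 8.1.7.5, SAP 6.0 and the cross-reference in SAP 11.3. **If** *on* is applied by date, the post-dose Day 1 sample can be taken as baseline, and a Day 1 worsening then goes uncounted unless a later value is worse still.

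The size in the trial is unknown. It would be tempting to say that all five tumor lysis analytes are affected in every subject, or mainly in the venetoclax arm. The documents support neither. The two shift criteria apply only to tests that CTCAE grades, the SAP does not list which those are, and no figure by arm is given. A subject whose grade rises further on a later day can still register a shift.

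The tables are descriptive, with no comparison between arms, and no efficacy analysis is touched. The correction is still worth making, because a stated rule disagrees with the protocol and can remove real shifts from a by-arm safety table.

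**What to change.** In SAP 11.3.2:
- Define the baseline grade as that of the last measurement before the first dose of any study drug, by date and time, in line with SAP 6.0 and protocol 8.1.7.5. Keep the existing provision for untreated subjects.
- State that post-dose Day 1 values count only as post-baseline.
- State that the worst-of-day rule does not pool pre-dose and post-dose values on Day 1.
- Give a rule for Day 1 samples with no recorded collection time.

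The cost is SAP wording and minor programming to use collection times. SAP 6.0 does not already provide this separation: it mentions the two draw times only to say that all values enter the TLS analysis.

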Appendix G. Tumor Lysis Syndrome Classification

Metabolic Abnormality	Criteria for Classification of Laboratory Tumor Lysis Syndrome*	Criteria for Classification of Clinical Tumor Lysis Syndrome**
Hyperuricemia	Uric acid > 8 mg/dL (475.8 µmol/liter)	N/A
Hyperphosphatemia	Phosphorus > 4.5 mg/dL (1.5 mmol/liter)	N/A
Hyperkalemia	Potassium > 6 mmol/liter	Cardiac dysrhythmia or sudden death probably or definitely caused by hyperkalemia
Hypocalcemia	Corrected calcium < 7.0 mg/dL (1.75 mmol/liter) or ionized calcium < 1.12 mg/dL (0.3 mmol/liter) [#]	Cardiac dysrhythmia, sudden death, seizure, neuromuscular irritability (tetany, paresthesias, muscle twitching, carpopedal spasm, Trousseau's sign, Chvostek's sign, laryngospasm, or bronchospasm), hypotension, or heart failure probably or definitely caused by hypocalcemia***
Acute Kidney Injury [!]	N/A	Increase in the serum creatinine level of 0.3 mg/dL (26.5 µmol/liter) or the presence of oliguria (average urine output of < 0.5 mL/kg/hr over a 6-hour period) [†]

* Laboratory TLS requires two or more metabolic abnormalities must be present during the same 24-hour period within 3 days before the start of therapy or up to 7 days afterward.

** Clinical TLS requires the presence of Laboratory TLS plus one or more findings from the Clinical TLS column.

Corrected calcium = measured calcium level in mg/dL + 0.8 × (4 – albumin in gm/dL).

! Acute kidney injury, unless attributable to another cause, represents clinical TLS even if criteria for laboratory TLS are not satisfied.

*** Not directly or probably attributable to therapeutic agent.

† If no institutional ULN is specified, age/sex ULN creatinine may be defined as follows: > 1 to < 12 years of age, both male and female, 61.6 µmol/L; ≥ 12 to < 16 years, both male and female, 88 µmol/L; ≥ 16 years, female 105.6 µmol/L, male 114.4 µmol/L.

Note: Laboratory tumor lysis syndrome and at least one clinical complication.

Cross reference: Howard SC, Jones DP, Pui CH. The tumor lysis syndrome. N Engl J Med. 2011;364(19):1844-54.

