Number and percentage of subjects meeting the Howard criteria for Laboratory TLS will be presented. Laboratory TLS requires two or more metabolic abnormalities must be present during the same 24-hour period. The evaluation period for TLS is after the first dose of study drug during Cycle 1 until 7 days from the first dose of study drug.

- uric acid > 476 mcmol/l,
- potassium > 6 mmol/l,
- inorganic phosphorus > 1.5 mmol/l
- calcium < 1.75 mmol/l.

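### The SAP's laboratory TLS count states its calcium limit without the albumin correction that Protocol Appendix G attaches to the same 1.75 mmol/L limit, so subjects can be misclassified in either direction

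*SAP*

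**What the plan says.** SAP section 11.3.2 undertakes this: "Number and percentage of subjects meeting the Howard criteria for Laboratory TLS will be presented". It lists four limits: uric acid above 476 µmol/L, potassium above 6 mmol/L, inorganic phosphorus above 1.5 mmol/L, and "calcium < 1.75 mmol/l". The counting rule is "Laboratory TLS requires two or more metabolic abnormalities must be present during the same 24-hour period", assessed from the first dose until 7 days after it. SAP section 6.0 adds a handling rule that begins "For analysis of tumor lysis syndrome (TLS) laboratory variables meeting the Howard criteria where multiple values were collected over the course of a day"; it says that every value is used and none is averaged. It does not mention albumin. SAP Table 10 lists calcium and albumin as separate tests.

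Protocol Appendix G gives the calcium criterion for laboratory TLS as "Corrected calcium < 7.0 mg/dL (1.75 mmol/liter) or ionized calcium" below 1.12 mg/dL (0.3 mmol/L). Its footnote supplies the formula: "Corrected calcium = measured calcium level in mg/dL + 0.8" × (4 − albumin in g/dL). Its cross-reference is "The tumor lysis syndrome. N Engl J Med. 2011;364(19):1844-54", which is also reference 4 in the SAP.

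**The concern.** The two documents name the same criteria and print the same number, but attach it to different quantities. The SAP exists to direct the programming, so someone working from its list would compare reported calcium with 1.75 mmol/L. Another programmer might take the Howard label to imply correction. The result would then depend on who read the text.

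Low albumin lowers measured calcium relative to corrected calcium. Because every draw counts, one low measured value is enough to set the calcium flag. If uric acid, potassium or phosphorus is also abnormal in the same 24 hours, the subject is counted as laboratory TLS although the Appendix G corrected-calcium criterion was not met.

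TLS is an important identified risk in Protocol section 3.0 and is the reason for the ramp-up and hospitalization, so its reported frequency should rest on the protocol's definition. Section 11.4 of the SAP also allows the laboratory summaries to be split by hepatic and renal impairment. If albumin differs between those groups, which is an inference and not something the documents show, an uncorrected limit would distort that split.

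**Working it through.** **Step 1. Do the limits match?**

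| Component | SAP 11.3.2 | Protocol Appendix G |
|---|---|---|
| Uric acid | > 476 µmol/L | > 8 mg/dL (475.8 µmol/L) |
| Potassium | > 6 mmol/L | > 6 mmol/L |
| Phosphorus | > 1.5 mmol/L | > 4.5 mg/dL (1.5 mmol/L) |
| Calcium | < 1.75 mmol/L, no qualifier | corrected < 7.0 mg/dL (1.75 mmol/L), or ionized < 1.12 mg/dL (0.3 mmol/L) |

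Three components carry over unchanged apart from rounding. Calcium keeps its number and loses both its qualifier and its alternative.

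**Step 2. Reproduce the protocol's figure.** With a calcium molar mass of 40.078 g/mol, 7.0 mg/dL × 10/40.078 = 1.747 mmol/L, which rounds to 1.75. The SAP limit is therefore the corrected-calcium limit in SI units. The protocol's own pair implies 1.75/7.0 = 0.25 mmol/L per mg/dL, used below.

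**Step 3. Size of the correction.** Correction = 0.8 × (4 − albumin) mg/dL × 0.25 mmol/L per mg/dL. The albumin values are assumed, because the documents give no distribution. The measured calcium that meets the corrected limit is below 7.0 − 0.8 × (4 − albumin) mg/dL.

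| Albumin (g/dL) | Correction (mg/dL) | Correction (mmol/L) | Measured calcium meeting the corrected limit | Measured values where SAP and corrected limit disagree (mmol/L) |
|---|---|---|---|---|
| 4.5 | −0.4 | −0.10 | < 7.4 mg/dL (1.85 mmol/L) | 1.75–1.85, SAP misses |
| 4.0 | 0 | 0 | < 7.0 (1.75) | none |
| 3.5 | +0.4 | +0.10 | < 6.6 (1.65) | 1.65–1.75, SAP flags |
| 3.0 | +0.8 | +0.20 | < 6.2 (1.55) | 1.55–1.75, SAP flags |
| 2.5 | +1.2 | +0.30 | < 5.8 (1.45) | 1.45–1.75, SAP flags |
| 2.0 | +1.6 | +0.40 | < 5.4 (1.35) | 1.35–1.75, SAP flags |

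**Step 4. One example each way.**
- Measured 1.60 mmol/L, albumin 3.0: 1.60 + 0.20 = 1.80. The SAP flags it; the corrected limit does not.
- Measured 1.80 mmol/L, albumin 4.5: 1.80 − 0.10 = 1.70. The corrected limit flags it; the SAP does not.

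**Step 5. From a calcium flag to a TLS count.** A wrong flag changes a subject's classification only if exactly one other component is abnormal in the same 24 hours. With none, the subject does not qualify either way. With two or more, the subject qualifies without calcium. Leaving out the ionized alternative can only lose cases.

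**Step 6. Are the data there?** Albumin is in the chemistry panel (Protocol Table 4). Section 5.3.1.1 schedules that panel on Cycle 1 Days 1 to 6 and Day 8, which covers most of the 7-day window. The TLS draws in section 6.1.7.1 (pre-dose and 6 to 8 hours post-dose) list calcium but not albumin. Ionized calcium is in neither Protocol Table 4 nor SAP Table 10.

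**The case against.** The SAP never says that calcium is total or uncorrected. It invokes the Howard criteria by name in two places and cites the publication that Appendix G cites, and its four numbers match Appendix G. The list can be read as shorthand for those criteria in SI units. This has some force: a careful programmer might apply the correction. But the SAP is where the rule should be settled, and its only stated calcium rule has no correction, so the wording still needs changing.

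A reader might go further and infer that TLS will be over-reported in low-albumin patients. The documents do not support that. A false call needs low albumin, a measured calcium inside the disagreement band, and one further abnormality within 24 hours. The error reverses when albumin is above 4 g/dL or when only ionized calcium is low. The net direction and the frequency are unknown, and the frequency may be zero. Nor is a corrected value of 1.80 mmol/L normal under the protocol: it only fails to meet the corrected limit, and the ionized limit could still be met.

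The consequence is also limited. SAP section 11.3 plans no statistical comparison of laboratory data between arms, and the same rule applies to both. The TLS adverse-event summary in SAP Table 9 uses a separate search and is unaffected, as are overall survival and every other efficacy endpoint. Appendix J already directs sites to look beyond measured calcium when albumin is low. All of this stands, and it keeps the point modest.

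**Conclusion.** The point holds as a mismatch of definitions. The criterion written in SAP section 11.3.2 is not the one in Protocol Appendix G, although both cite the same source, and the SAP gives no reason for departing from it. Per sample, the gap is 0.20 mmol/L for each 1 g/dL of albumin away from 4. That is over-flagging bands of 0.10, 0.20 and 0.30 mmol/L at albumin 3.5, 3.0 and 2.5 g/dL, and an under-flagging band of 0.10 at 4.5 g/dL. These figures rest on the Appendix G formula and on assumed albumin values. The effect on the laboratory TLS count cannot be computed, because the documents give no joint distribution of calcium, albumin and the other components. The supportable statement is that laboratory TLS can be misclassified in either direction, within a descriptive safety summary.

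**What to change.** Replace the calcium bullet in SAP section 11.3.2 with: albumin-corrected calcium < 1.75 mmol/L by the Appendix G formula, using albumin from the same sample or, if absent, from the nearest chemistry sample within a stated window (for example 24 hours); ionized calcium by the Appendix G limit only where it was recorded.

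Add a rule for missing albumin. One option is to treat the calcium component as not assessable and report how many subjects this affects; another is to use measured calcium and mark those cases. Either serves if it is written down beforehand. If measured calcium was intended, the SAP should say so, give the reason, and stop labelling the count as the Howard criteria.

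The cost is a few lines of SAP text and one derived variable, with no new data collection. The drawback is the pairing rule: because the TLS draws do not list albumin, some post-dose calcium values will be corrected with albumin taken at another time that day. Ionized calcium will probably be sparse, since it is not a planned test.

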3.0 Introduction

This statistical analysis plan (SAP) describes the full efficacy and safety statistical analyses for venetoclax Study M16-043 (Viale-c) Protocol Amendment 4 dated 29 November 2018. It will provide details of statistical methods and describe analysis conventions to guide the statistical programming work.

Unless noted otherwise, all analyses will be performed using SAS[®] version 9.3 or later (SAS Institute Inc., Cary, NC 27513) under the UNIX operating system.

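### The SAP's laboratory TLS rule applies the albumin-corrected calcium cut-off of Protocol Appendix G to calcium with no stated correction and omits the ionized-calcium alternative

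*SAP*

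**What the plan says.** SAP 11.3.2 sets the output: "Number and percentage of subjects meeting the Howard criteria for Laboratory TLS will be presented". It then requires two abnormalities together: "Laboratory TLS requires two or more metabolic abnormalities must be present during the same 24-hour period". Four limits follow, for uric acid, potassium, inorganic phosphorus and calcium. The calcium line is "calcium < 1.75 mmol/l".

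Protocol Appendix G defines the same condition from the same cited source. Its calcium entry begins "Corrected calcium < 7.0 mg/dL (1.75 mmol/liter" and continues with an alternative: ionized calcium below 1.12 mg/dL (0.3 mmol/L). A footnote gives the correction: "Corrected calcium = measured calcium level in mg/dL + 0.8 × (4 – albumin in gm/dL".

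SAP 6.0 has one convention specific to TLS laboratory values. It covers repeated draws within a day, before dosing and "6 – 8 hours post dose), all values will be used and no averages will be taken". It does not mention correction. No other section of the SAP defines a corrected-calcium variable or uses ionized calcium.

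**The concern.** The two documents use one number for two different quantities. The SAP describes its own purpose this way: "It will provide details of statistical methods and describe analysis conventions to guide the statistical programming work". An explicit list of four numeric limits is what a programmer will code, and it names calcium alone.

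Measured calcium understates corrected calcium when albumin is below 4 g/dL, so the SAP list can call a value abnormal that Appendix G would not. Above 4 g/dL the error runs the other way. Because SAP 6.0 uses every value without averaging, one uncorrected reading below the limit is enough to meet the calcium criterion.

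The protocol treats the difference as relevant in practice. In its hypocalcemia guidance, Appendix J tells sites to work out corrected calcium and to check ionized calcium when albumin is low.

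What is at stake is the SAP's laboratory-based count for a risk that the protocol introduction names as important for venetoclax. SAP 11.4 also allows the laboratory analyses to be summarized by baseline hepatic and renal impairment. The error depends on albumin, so it need not be equal across subgroups whose albumin differs.

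**Working it through.** **Inputs**

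- SAP 11.3.2: calcium limit 1.75 mmol/L, no correction stated.
- Appendix G: corrected-calcium limit 7.0 mg/dL, printed as 1.75 mmol/L; correction 0.8 mg/dL per 1 g/dL of albumin below 4.
- Albumin values: assumed, for illustration. The documents give no distribution.

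**Step 1. Reproduce the printed cut-off.** With 4.0078 mg/dL per mmol/L (atomic mass of calcium 40.078), 7.0 / 4.0078 = 1.747, which rounds to 1.75 mmol/L. The conversion is sound, and the SAP's figure is the Appendix G corrected-calcium cut-off. Appendix G's own factor is 1.75 / 7.0 = 0.25 mmol/L per mg/dL, used below.

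**Step 2. Find the measured calcium that meets Appendix G.** Let M be measured calcium (mg/dL) and A albumin (g/dL). Appendix G requires M + 0.8 × (4 − A) < 7.0, so M < 7.0 − 0.8 × (4 − A).

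| Albumin, g/dL (assumed) | Appendix G limit on M, mg/dL | mmol/L (× 0.25) | SAP limit, mmol/L | Gap, mmol/L |
|---|---|---|---|---|
| 4.5 | 7.4 | 1.85 | 1.75 | 0.10 (SAP under-flags) |
| 4.0 | 7.0 | 1.75 | 1.75 | 0 |
| 3.5 | 6.6 | 1.65 | 1.75 | 0.10 (SAP over-flags) |
| 3.0 | 6.2 | 1.55 | 1.75 | 0.20 (SAP over-flags) |
| 2.5 | 5.8 | 1.45 | 1.75 | 0.30 (SAP over-flags) |
| 2.0 | 5.4 | 1.35 | 1.75 | 0.40 (SAP over-flags) |

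**Step 3. The formula in mmol/L.** 0.8 × 0.25 = 0.2, so corrected calcium = measured calcium + 0.2 × (4 − A). Each 1 g/dL of albumin away from 4 shifts the limit by 0.20 mmol/L.

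**Step 4. One reading.** Measured 1.70 mmol/L at albumin 3.0 g/dL: 1.70 + 0.2 × 1 = 1.90 mmol/L. The SAP list flags it because 1.70 < 1.75. Appendix G's corrected route does not, because 1.90 > 1.75. Only a low ionized calcium would make it abnormal under Appendix G.

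**Step 5. From one reading to a subject's status.** Two abnormalities are needed in the same 24 hours. A wrongly flagged or missed calcium changes the subject's status only if exactly one of uric acid, potassium and phosphorus is also abnormal in that period, and the subject does not qualify in some other 24-hour period. If none of the three is abnormal, or two or more are, calcium makes no difference.

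**Step 6. Are the data there to correct?** Protocol 6.1.7.1 lists the TLS draws: "TLS chemistry tests to be drawn (calcium, inorganic phosphorus, potassium, uric acid, and creatinine) on the first day of venetoclax/placebo dosing" and on each new-dose day, before dosing and 6 to 8 hours after. Albumin is not in that set. It is in the Table 4 chemistry panel, which Section 5.3.1.1 schedules on Cycle 1 Days 1 to 6 and Day 8. The standard ramp-up takes Days 1 to 4, so each of its four post-dose draws has a scheduled same-day albumin. Ionized calcium is not in Table 4, so it will exist only where a site measured it.

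**The case against.** The strongest reply is that the governing sentence in SAP 11.3.2 names the Howard criteria, SAP 6.0 names them again, and the SAP reference list cites the source. On that reading the four limits are an abbreviation, and an informed programmer would supply the correction. This has some force: the documents do not show which calcium was programmed. It does not rescue the text. A numeric list in a document written to guide programming is a rule, and this one gives a different answer from the protocol's definition. A programmer who did infer the correction would still find no formula, no unit conversion and no albumin-pairing rule in the SAP.

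A second reply is that Appendix G does not make the albumin correction compulsory, since low ionized calcium also qualifies. That is right, and it limits the claim: a reading in the over-flagged band is wrong under Appendix G only if ionized calcium is not low. As Table 4 does not include ionized calcium, correction is the route that works for most readings.

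Third, separate rows for calcium and albumin in SAP Table 10 prove little. That table serves the mean-change summaries, not the TLS derivation. The point does not rest on it.

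A reader might also suspect the SAP's phosphorus limit of 1.5 mmol/L. It matches the mmol/L figure printed in Appendix G, so the two documents agree there and it should stay.

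**Conclusion.** The SAP calcium line is wrong as written. This is a mismatch of definition between SAP and protocol, not an arithmetic error: the unit conversion reproduces. The size is 0.20 mmol/L in the calcium limit per 1 g/dL of albumin from 4 g/dL, assuming the line is coded literally and ionized calcium is unavailable or not low.

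The consequence is small. The output is descriptive, SAP 11.3 rules out statistical comparison of laboratory data between arms, and the same rule applies to both arms. The TLS adverse-event summary in SAP Table 9 uses its own search criteria and is unaffected, as are all efficacy analyses.

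A reader might infer that the trial's laboratory TLS count is inflated. The documents do not support that. They give no albumin or calcium distributions, they do not show what was programmed, the error reverses above 4 g/dL, and a second abnormality is needed. No number of misclassified subjects can be derived.

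**What to change.** Replace the calcium line in SAP 11.3.2 with wording such as:

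*Albumin-corrected calcium < 1.75 mmol/L, where corrected calcium (mmol/L) = measured calcium (mmol/L) + 0.2 × (4 − albumin in g/dL; divide g/L by 10), or ionized calcium < 0.3 mmol/L where available, per Protocol Appendix G. Use same-day albumin or, if none, the most recent earlier albumin within 3 days. Report the number of subjects with no usable albumin.*

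The 3 days are a suggestion. Some stated limit is needed, because an open look-back could carry forward a screening value taken up to 21 days before randomization.

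The cost is one SAP wording change and one derived variable. No new sample and no protocol amendment are needed. The protocol's amendment summary says the final analysis is complete, so the practical step is to check which calcium was programmed and, if it was uncorrected, rerun the table on the collected data. One limitation remains: a same-day albumin drawn before IV hydration may be higher than at the post-dose draw, which would make the correction slightly too small.
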